### **1.1.6 Severe acute respiratory syndrome due to the evolution of COVID-19**

The *Severe Acute respiratory syndrome* (SARS) or Severe Acute Respiratory Syndrome (SARS) is one of the most frequent causes of hospital admission followed by death in patients affected by Covid-19. According to the Ministry of Health, the definition of SARS is said to be an acute respiratory disease characterized by fever above 38°, cough, dyspnea, increased respiratory rate (>25 breaths/minute), and may also present with hypotension and even, gastrointestinal signs and symptoms (LANA et al. 2020).

Assuming the evolution of the disease, the clinical picture worsens as the process of acute hyperinflammation of the tissue and pulmonary edema occurs, resulting in exacerbated permeability due to the injury, and often disruption, of the alveolar capillary barrier. According to Almeida (2018), this process of pulmonary inflammation generates the release of inflammatory molecules such as cytokines , which are responsible, respectively, for the activation and recruitment of alveolar macrophages and neutrophils in the lungs, triggering the release of leukotrienes , oxidants, platelet activation and proteases. Ware ( 2020 ) explains that these substances cause damage to the capillary endothelium and alveolar epithelium, so the barriers between capillaries and air spaces are broken. As a result, the air spaces and the interstitium are flooded by edematous fluid, proteins and other cellular debris,

culminating in surfactant disruption, collapse of air spaces, misalignment between ventilation x perfusion and pulmonary hypertension (ALMEIDA, 2018, CORDIOLI, 2012). ) .

Ware (2020) also describes that, in the evaluation of lung mechanics in the first 24 hours after admission to the ICU, it shows that lung compliance is decreased, along with a series of factors, suggesting a mortality of 40% to 60% in these individuals. This survival rate, evidenced in Covid-19, suggests a pathophysiology of pulmonary microvascular thrombosis due to coagulation deregulation and fibrinolysis , accompanied by lung injury, indicators of major deleterious effects in recovered individuals (CORDIOLI, 2012, REIS, LIMA, 2020, WARE, 2020) . In general, the consequences left in the body of individuals considered recovered represent persistent respiratory dysfunctions, mainly in the tissues and organs of the respiratory system, accompanied by important deficits not only directly linked to respiratory capacity during physical activities, but also, and perhaps mainly linked to BADL (basic activities of daily living), which involve basic self-care (ALMEIDA, 2018, DORNELES, 2018) .

### **1.1.7 Post-COVID-19 Syndrome**

According to the Ministry of Health's Surveillance System, the survival rate of individuals who have experienced the most severe form of Covid-19 is approximately 50%. Although there are few published studies on the sequelae left by SARS-CoV-2 in the body, it is already known that the disease leaves traces in many systems (LANA et al. 2020). In the study by Juárez-Belaúnde , Colorme font *et al* . (2020), in their report to the journal of Neurologia, states that the pathophysiological process of the disease comes from an inflammatory response that mainly affects the respiratory system. However, the author emphasizes that new studies have been identifying sequelae of great significance, also in the cardiovascular, neurological and musculoskeletal systems. As described by the WHO, the probability of deficits in these systems increases in individuals who have undergone periods of ICU stay, combined with the need to use respirators. As a result, the morbidities acquired in the process leave important impacts on the functional and cognitive capacities of recovered individuals (GREVE, BRECH, *et al* . , 2020, PAHO/WHO, 2020) .

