## Summary

**Introduction:** COVID-19 is an emerging pandemic disease caused by severe acute respiratory syndrome (SARS-CoV-2). Although most patients infected with SARS-CoV-2 are asymptomatic or have mild symptoms, some patients develop severe symptoms that can long-term impair their quality of life and functional capacity. SARS-CoV-2 is closely related to severe acute respiratory syndrome (SARS) with direct and indirect effects on several systems, especially the musculoskeletal system, in addition to the respiratory system. Some of these symptoms persist for a long time, called Post-Covid-19 Syndrome, directly interfering with the functional capacity and quality of life of these patients. Pilates exercises focus on breathing, postural symmetry, trunk stabilization, flexibility, joint mobility and strengthening through the full range of motion of all joints and not isolated muscle groups. **Objectives:** The objective of this study will be to evaluate the clinical and functional effects of a Pilates exercise program for patients with Post-Covid-19 syndrome after a period of intensive care admission and invasive mechanical ventilation. **Methods:** The study will be a clinical, randomized and controlled trial. 48 patients of both sexes, over 18 years of age, who have developed the severe form of COVID-19 and required at least 7 days of invasive mechanical ventilation will be recruited. Patients who currently require supplemental oxygen at home and who present motor, cognitive or neurological alterations that prevent the practice of Pilates will be excluded. They will be previously randomized in a 1:1 ratio by electronic system and blindly allocated to the intervention group that will perform an exercise protocol based on the Pilates method, 2x/week, for 12 weeks in therapeutic sessions of identical protocols lasting 60 min. All patients will be evaluated before and after for peripheral muscle strength and endurance, post-Covid-19 functional status, dyspnea, fatigue and quality of life. Data analysis will be performed using the SPSS 23.0 program ( *Statistical Package for Social Sciences* ). Descriptive analysis will be performed for all variables (mean and standard deviation). *General Linear Model* ( GLMs ) with mixed design will be performed to compare treatment effect size between groups. The *pairwise comparison comparisons* ) will be performed to verify the mean difference between the Pilates Group and the Control Group in all variables in each period independently. Intention-to-treat analysis was used using the *Last method. observation Carried Forward* (LOCF) for lost participant data. A significance level of 0.05 and a confidence interval of 95% will be adopted. **Results:** The expected results are based on the alternative hypothesis that Pilates exercises are clinically effective, improving functional performance, exercise tolerance, balance, reducing symptoms and improving the quality of life of patients with symptoms of Post-Covid-19 Syndrome.

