Not infrequently, some individuals who reach the most severe condition, approximately 5%, develop very uncomfortable systemic complications, conferring greater morbidity to the disease progression. According to Merkel *et al.* (2020) and Puntmann *et al.* (2020), such complications can be: severe pneumonia, progressive respiratory failure due to alveolar damage, ARDS, acute renal failure, heart failure, liver failure, sepsis and septic shock, thromboembolic events, bacterial or fungal infections , multiple organ failure , persistence of hyperthermia, decreased lymphocyte and leukocyte counts and new pulmonary infiltrates.

Taking this context into account, complications from Covid-19 usually occur in individuals who have risk factors and previous comorbidities such as: age >60 years, diabetes mellitus, arterial hypertension, smoking, obesity (BMI > 40), COPD, disease chronic kidney disease, chronic liver disease, immunodeficiency and cerebrovascular disease. So much so that, in the study by Pegado (2020), it was observed that the exacerbation of adjacent diseases and the findings of respiratory rate >30 RM and  $\text{SatO}_2 < 93\%$ ,  $\text{PaO}_2 / \text{FiO}_2 < 300$ , represented a poor prognosis, accompanied by a rate of mortality from SARS around 10%. Therefore, it is suggested that there is a strong association that other unfavorable pre-existing clinical conditions combined with Covid-19 significantly favor the worsening of the clinical condition, and consequently, considerably increase the mortality rate of these individuals (IOANNOU, LOCKE, *et al.* , 2020, PUJADAS, CHAUDHRY, *et al.* , 2020) .

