### **2.3.2 Inclusion criteria**

1. Patients with a previous diagnosis of COVID-19, who required hospitalization and required invasive mechanical ventilation for at least 7 days and who were discharged between August and December 2021 to minimize regression to mean;
2. Both sexes;
3. Older than 18 years.

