### **2.3.3 Exclusion criteria**

1. Need for supplemental home oxygen;
2. Motor or neurological or cognitive alteration that contraindicates the practice of Pilates .
3. Persistence of clinical signs of deep vein thrombosis
4. Upper limb dynamometry < 14 kg for men and < 7 kg for women would indicate very marked peripheral muscle weakness and would therefore contraindicate Pliates at the moment.

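### The exclusion criteria do not ask about a known cardiac contraindication to effort, although the protocol itself names cardiovascular sequelae as important in this population

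*Combined protocol and SAP*

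**What the plan says.** Section 1.1.7 states that "new studies have been identifying sequelae of great significance, also in the cardiovascular, neurological and musculoskeletal systems". It continues that "the probability of deficits in these systems increases in individuals who have undergone periods of ICU stay, combined with the need to use respirators". Section 1.1.4, on the most severe cases, lists complications that include "ARDS, acute renal failure, heart failure, liver failure, sepsis and septic shock, thromboembolic events".

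The trial enrols patients who "required invasive mechanical ventilation for at least 7 days" (2.3.2), with no upper age limit.

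Section 2.3.3 gives four exclusions:

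1. need for oxygen at home;
2. "Motor or neurological or cognitive alteration that contraindicates the practice of Pilates";
3. "Persistence of clinical signs of deep vein thrombosis";
4. grip strength under 14 kg in men or 7 kg in women, which "would indicate very marked peripheral muscle weakness" and is treated as a reason not to do Pilates for now.

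The Summary and the Abstract repeat the oxygen criterion and exclusion 2; patients who "present motor, cognitive or neurological alterations that prevent the practice of Pilates will be excluded". A clinical history is taken at the initial assessment (2.3.5), but no eligibility rule is tied to it.

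**The concern.** The protocol groups three body systems as sites of significant sequelae: cardiovascular, neurological and musculoskeletal. Exclusion 2 calls for a judgement on the neurological system and, if motor alteration is read that way, on the musculoskeletal one. It does not call for one on the cardiovascular system. It also refers only to Pilates, whereas both arms perform a maximal quadriceps strength test and an endurance test to failure.

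What is at stake is patient safety at entry. No claim is made that the trial's result would be biased, or about how often such patients would present.

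**Working it through.** **Step 1: does any entry criterion reach a known cardiac contraindication?**

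| Criterion | What it asks | Reaches the heart? |
|---|---|---|
| Inclusion criteria (2.3.2) | Ventilated COVID-19, discharge window, sex, age | No |
| Exclusion 1 | Home oxygen | Only incidentally |
| Exclusion 2 | Motor, neurological or cognitive contraindication to Pilates | No |
| Exclusion 3 | Signs of deep vein thrombosis | No; it is venous |
| Exclusion 4 | Fixed grip threshold | Only incidentally |

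Home oxygen and low grip strength may remove some cardiac patients, and 2.3.6.1 treats grip strength as a marker of general health. Neither asks about the heart. There is no general clause on medical contraindication to exercise, and the Summary and Abstract add none.

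**Step 2: do other provisions act as an entry rule?**

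- The suspension statement (2.3.4) applies once a risk or damage is noticed during the research.
- The Borg scale (2.3.8) controls intensity in the Pilates sessions only, so it does not cover the quadriceps tests.
- Sessions are led by a specialised physical therapist in groups of up to three (2.3.11). This governs conduct.
- A pulse oximeter appears in the budget table (2.7) with no stated use.
- Recruitment is through a hospital and its multidisciplinary follow-up clinic (2.3.1). This makes known problems more likely to be on record but sets no rule.
- The 90-day wait after discharge (2.5.4) is justified by immobility complications and by making the groups similar, not by cardiac status.

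None of these decides cardiac eligibility.

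**Step 3: what exertion would an eligible patient face?** These are planned maxima.

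- 1RM test, up to five attempts (2.3.6.2), before and after (Summary): 5 × 2 = 10 attempts.
- Endurance test to failure at 40% of 1RM (2.3.6.3), before and after: 1 × 2 = 2 tests.
- Pilates arm, twice a week for 12 weeks (2.3): 2 × 12 = 24 sessions.
- Loaded time, 40 min per session (2.3.11): 24 × 40 = 960 min = 16 h.

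**Step 4: trial totals.** The plan's sample size (2.5.1) reproduces. A two-sided two-sample t-test with d = 0.93, α = 0.05 and power 0.80 gives n = 19.16 per group, rounded up to 20; 20 × 1.20 = 24 per group, or 48 in all. Section 2.3 gives 60, so both are shown. The second row in each pair assumes that the whole loss allowance (4 of 24 = 16.7%, or 5 of 30) is used before the post-test, and it counts sessions only for completers with full attendance.

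| Enrolled | Scenario | Each quadriceps test | Pilates patient-sessions |
|---|---|---|---|
| 48 | No losses | 48 × 2 = 96 | 24 × 24 = 576 |
| 48 | 4 of 24 lost per arm | 48 + 40 = 88 | 20 × 24 = 480 |
| 60 | No losses | 60 × 2 = 120 | 30 × 24 = 720 |
| 60 | 5 of 30 lost per arm | 60 + 50 = 110 | 25 × 24 = 600 |

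The totals cover all patients, not those with a cardiac contraindication.

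**The case against.** The strongest reply is that this is wording without a shown consequence. The change reaches only conditions that are already known, in patients who come from a hospital and specialist follow-up, give a history, and are at least 90 days past discharge. Clinicians would probably not enrol someone with a recognised contraindication. The statements in 1.1.4 and 1.1.7 are literature review, and the list in 1.1.4 also names renal and liver failure, so the choice of the heart may seem arbitrary. Exclusions 3 and 4 also involve a clinical reason not to exercise. The two tests are knee-extension tests with rest periods, not whole-body maximal efforts. The suspension statement needs only a perceived risk, not an event.

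Much of this stands as a limit on severity. The number of patients affected is unknown and may be zero, and the documents do not say that these tests are hazardous in cardiac disease. The session totals fall if attendance is incomplete. Equating motor with musculoskeletal is an interpretation of a translated text. The consent form was not available for review, so nothing is said about precautions it may contain.

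The gap in the entry rule remains. The plan chose to write down its motor, neurological, cognitive, thrombosis and grip rules and did not leave them to judgement. The heart is singled out because 1.1.7 names the cardiovascular system together with the two systems that exclusion 2 addresses. Exclusion 3 concerns veins, exclusion 4 is a fixed threshold, and a suspension statement is not an eligibility criterion.

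**Conclusion.** The concern holds, as a minor one. The written criteria admit a patient with a known cardiac contraindication to effort who clears all four exclusions, in a population that the protocol itself describes as more prone to cardiovascular deficits. The exertion in question is at most 10 strength-test attempts and two endurance tests per patient in either arm, plus up to 16 hours of loaded exercise in the Pilates arm. This conclusion rests on the eligibility text as written. The trial totals also rest on the stated assumptions about timing of losses and attendance. No prevalence, event risk or expected harm can be derived from the documents.

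**What to change.** Reword exclusion 2 in 2.3.3 to: *motor, neurological, cognitive or cardiovascular alteration that contraindicates Pilates or the 1RM and endurance tests*. Make the same change where the criterion is repeated in the Summary and the Abstract. State that it is judged from the clinical history collected under 2.3.5, before the first 1RM test and before allocation is disclosed, in the same way for both arms.

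The cost is a few words in three places, with no added staff, screening or procedure. A few candidates may be excluded and the study population becomes slightly narrower. The change relies on clinical judgement, acts only on known conditions and would not detect undiagnosed heart disease.

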### **1.1.8 respiratory disorders**

fibrotic normalities , previously associated with the idiopathic cause, are the main consequences left by the passage of Covid-19, so that its manifestations can result from any stage, being evidenced more frequently in cases that have undergone the most severe form of the disease. illness. Consequently, the lung damage caused by SARS-CoV-2 infection in the acute phase results from the combination of some expected clinical manifestations, such as: edema formation, alveolar release of epithelial cells and deposition of hyaline material in alveolar membranes . (POGLITSCH, *et al.* , 2020) . During the 2nd and 4th weeks, the lungs show signs of fibrosis, characterizing the next phase of the infection, where fibrin deposition occurs, infiltration of inflammatory cells and fibroblasts adjacent to the epithelial cells in the alveolar spaces (HULL, LLOYD, *et al.* , 2020) .

A little further on, during the 6th to 8th week, the lung tissue becomes fibrotic , in addition, bilateral lesions tend to be observed. In this context, Raghu and Wilson (2020) observed in their study that individuals, after hospital discharge, present restrictive abnormalities such as reduced diffusion capacity and small airway obstruction. Some authors also suggest that these abnormalities may be common in lung function, especially in individuals who have reached the most severe form of Covid-19, due to high inflammatory rates and pulmonary fibrosis.

Despite what is already evidence on the multisystem sequelae of Covid-19, several other studies are emerging around the sequelae left in the respiratory system after infection by the SARS-CoV-2 Coronavirus , suggesting that these may vary in individuals who have had it. mild, moderate or severe frames. The same authors also state that the resolution of the abnormalities may occur within the next 6 to 12 months after the infection, or even become permanent (HADAYA, BENHARASH, 2020) .

Another consequence of SARS-Cov-2 infection on respiratory capacity is the damage generated in neural tissue by inflammatory events. This in turn receives information from mechanoreceptors and chemoreceptors in the lungs and/or provides innervation to organs, airway smooth muscle, glands and vasculature . Strike, Brech *et al.* (2020) report in their study that some complications and/or deficits left in respiratory capacity may be the result of cardiorespiratory arrest after damage to the innervations of the heart, lungs and other organs of the cardiorespiratory system, as well as loss of neuromuscular function and muscle trophism . . Thus, it can be considered that decreased cardiorespiratory function, decreased inspiratory muscle strength and, consequently, functional capacity are linked to the worsening of

symptoms resulting from SARS-Cov-2 infection in neural tissue linked to organs and/or structures in the system. respiratory system (HADAYA, BENHARASH, 2020, ZOUFALY, POGLITSCH, *et al.* , 2020) .

### 1.1.8.1 Neurological Dysfunctions

There are some hypotheses and speculations about the way in which the virus accesses the nervous system, the main one being the one that defends the idea that one of the transsynaptic pathways of the vagus nerve would be responsible (INCIARDI, LUPI, *et al.* , 2020) . , LU, LI, *et al.* , 2020) . This hypothesis is due to the fact that its innervation involves the lower part of the airways through the nasal and olfactory epithelium (GREVE, 2020; WEI, LIU, *et al.* , 2020) . But there are differences between the authors, so much so that some still discuss a second hypothesis, which the spread would occur via hematogenous , with the virus crossing the blood -brain barrier . (MATSCHKE, LÜTGEHETMANN, *et al.* , 2020) . However, when observing the neural tissue infected by SARS-CoV-2, the induction of cellular apoptosis by the virus was observed, where the mechanisms of apoptosis are similar to those of demyelinating diseases , which I could give more support to the first hypothesis (JUÁREZ-BELAÚNDE , COLOMER FONT, *et al.* , 2020, MATSCHKE, LÜTGEHETMANN, *et al.* , 2020) .

Taking into account individuals hospitalized due to severe Covid-19 infection, they may be susceptible to central and peripheral nervous system injuries, so that their inherent neurological sequelae are not limited to functional damage only, but complications such as confusional syndromes , vascular accident. cerebral palsy (CVA), encephalopathies, encephalitis, polyneuropathy and Guillan -Barre syndrome , confirming a significant functional impact and also quality of life (INCIARDI, LUPI, *et al.* , 2020, JUÁREZ-BELAÚNDE, COLOMER FONT, *et al.* , 2020) .

Among the main neurological complications, it was observed that about 20% of individuals affected by Covid-19 had among the main signs and symptoms, namely: changes in consciousness, seizures or epileptic status, paralysis, CVA (cerebrovascular accident), infectious neuropathy, peripheral polyneuropathy , in addition to possible necrotizing myopathy (LU, LI, *et al.* , 2020, SHAHJOUEI, NADERI, *et al.* , 2020) . However, the author considers it pertinent to note that the so-called critically ill polyneuropathy , in general an infectious mixed sensorimotor neuropathy,

by itself already causes axonal degeneration , and necrotizing myopathy , in turn, can cause fatty degeneration, hypotrophy and fibrosis. Such conditions are frequently observed, respectively, in 46% and 48% to 96% of individuals who experience prolonged ICU stay (GREVE, BRECH, *et al.* , 2020) .

### **1.1.8.2      musculoskeletal disorders**

As is widely known, the condition of physical inactivity, caused by hospitalization in the ICU (or even social isolation), can significantly impact the muscle homeostasis of individuals. In this context, the inflammatory process caused by Covid-19 infection promotes musculoskeletal consequences that are often catastrophic, impacting and can last for a long period of patients' lives, drastically reducing their quality of life. This condition seems to be more evident in individuals who remain in hospital for long periods, however, the author explains that this process involves several conditions to which individuals are exposed, such as the inflammatory process, immobility, in addition to insufficient nutritional and caloric support, apart from The administration of corticosteroids is often carried out without such criteria, given the complex contexts in which patients are inserted (GREVE, BRECH, *et al.* , 2020) .

Even before the Covid-19 pandemic, it was already widely known that patients who are exposed or subjected to long periods of immobility, precisely due to the absence of exposure to mechanical discharges, end up triggering an adaptive response, which, among other things, includes: of protein synthesis, increased degradation and apoptosis of muscle cells (sarcomeres), leading to the dreaded sarcopenia. When such a condition sets in, there is inevitably a loss of homeostasis in the renewal of muscle tissue, accelerating the process of hypotrophy and loss of muscle strength (NUNES, HERVÉ, *et al.* , 2020) .

Strike, Brech *et al.* . (2020) also describe in their study that in the first week of hospitalization, a loss of up to 20% of thigh muscle mass can already occur in septic individuals in the ICU. The author also points out that one week in bed can generate a 30% reduction in muscle strength, followed by an additional 20% loss each following week. In view of this, it is concluded that the loss of muscle mass and strength will directly impact the physical capacity or even daily activities of these individuals, generating a significant negative impact on the quality of life of patients affected by

Covid-19, and who have experienced such a situation (CORRÊA , KARLOH, *et al.* , 2011, NUNES, HERVÉ, *et al.* , 2020) .

